**Figure 1: Schematic Diagram**

#### 4.1.2. Randomisation and Blinding

At the end of the Screening period, eligible patients will be randomised to receive either Presendin or matching placebo in a 1:1 ratio using a computer system to generate randomisation codes.

Investigators and other site personnel, patients, contract research organisation and Sponsor personnel will be blinded regarding the treatment during the randomised period. Only designated unblinded staff, not involved in the operational conduct of the trial, will be aware of the randomisation codes.

The placebo will have the same appearance and reveal no differences, during administration, to either the Investigator or the patient.

#### 4.1.3. Duration of Patient Participation

The duration of the trial for each patient will be up to 30 weeks, which includes a 1-week screening period, a 24-week randomised treatment period and a treatment follow-up period of 5 weeks.

Study Number: INVEX-CLIN-IIH-301 Protocol	Compound No.: Presendin
	Version: 5.0 for EU countries dated 08Dec2022

## **4.2. Stopping Rules**

### **4.2.1. Trial Stopping Rules**

There are no trial-specific stopping rules. The Sponsor maintains the right to stop the trial at any point. If this is done, then the Sponsor will provide the Investigators with the rationale for such early termination.

### **4.2.2. Individual Stopping Rules**

Patients will be withdrawn from the trial medication if they are unable to tolerate the trial medication and will continue to attend trial visits as per protocol. See Section 11 for further details. A Data Safety Monitoring Committee (DSMC) will be involved in decisions for patient safety (Section 14.6).

## **4.3. End of Trial**

The end of trial is defined as last patient last visit.

## **5. TRIAL POPULATION**

### **5.1. Number of Patients**

It is anticipated that approximately 350 patients will be required to enter the screening phase for 240 patients to be randomised into the treatment phase.

### **5.2. Eligibility Criteria**

#### **5.2.1. Inclusion Criteria**

Patients must not be enrolled unless they meet all the following criteria:

1. Age  $\geq$ 18 years at the time of consent
2. Diagnosis of new IIH by consensus criteria (see Section 16.2, Appendix 2), including normal structural brain imaging (excluding features of raised intracranial pressure and incidentalomas), including either magnetic resonance venography or computed tomographic venography to exclude thrombosis and no evidence of a secondary causes of raised intracranial pressure
3. Newly diagnosed patients with screening commenced no more than 4 weeks after the diagnostic LP

Study Number: INVEX-CLIN-IIH-301 Protocol	Compound No.: Presendin
	Version: 5.0 for EU countries dated 08Dec2022

4. Lumbar puncture opening pressure  $\geq 25$  cm cerebrospinal fluid (CSF) at diagnosis
5. Presence of bilateral papilloedema (Frisén grade  $\geq 1$ ). Verification of papilloedema by the OCT Reading Centre. Where there is uncertainty fundus photography and/or ultrasound scan (B scan) of the optic nerves should be conducted for evaluation by the Independent Adjudication Committee (IAC)
6. Perimetric Mean Deviation (PMD) defined as between -2 to -7 decibels (dB) in at least one eye. Eyes meeting this criteria will be defined as ‘study eyes’
7. Reproducible visual loss present on automated perimetry including no more than 15% false positive responses, (reliability confirmed by the Visual Field Reading Centre) in study eyes
8. Two or more headache days over the 7-day period prior to screening and also the patient must meet this criterion during the 7-day screening period
9. Females of childbearing potential must have a negative pregnancy test and must agree to use a highly effective birth control method (failure rate less than 1% per year when used consistently and correctly – see Section 16.8, Appendix 8 for further details) during the whole trial duration including the last follow-up visit (12 weeks after ceasing drug). Female patients who are lactating must agree to stop breast-feeding. Or female patients of non-childbearing potential (defined as pre-menopausal females with a documented tubal ligation or hysterectomy; or post-menopausal females defined as 12 months of amenorrhoea [in questionable cases a blood sample with simultaneous follicle stimulation hormone (FSH) 25-140 IE/L and oestradiol  $<200$  pmol/L is confirmatory])
10. Male patients with a female partner of childbearing potential must commit to practice methods of contraception (e.g., condom, vasectomy) and abstain from sperm donation during the trial including the last follow-up visit (12 weeks after ceasing drug). Their partners, if they are women of childbearing potential, must agree to practice contraception and to use a highly effective method of contraception during the trial, including the last follow-up visit (12 weeks after ceasing drug)
11. Able to provide written informed consent

Note: This would restrict the ability of vulnerable patients, such as inmates of psychiatric wards, prison or state institutions, with commitment to an institution or a patient who is detained or committed to an institution by a law court or by legal authorities to be included on the grounds that informed consent could not be assumed.

Study Number: INVEX-CLIN-IIH-301 Protocol	Compound No.: Presendin
	Version: 5.0 for EU countries dated 08Dec2022

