  10. Male patients with a female partner of childbearing potential must commit to practice methods of contraception (e.g., condom, vasectomy) and abstain from sperm donation during the trial including the last follow-up visit (12 weeks after ceasing drug). Their partners, if they are women of childbearing potential, must agree to practice contraception and to use a highly effective method of contraception during the trial, including the last follow-up visit (12 weeks after ceasing drug)
  11. Able to provide written informed consent

Note: This would restrict the ability of vulnerable patients, such as inmates of psychiatric wards, prison or state institutions, with commitment to an institution or a patient who is detained or committed to an institution by a law court or by

Study Number: INVEX-CLIN-IIH-301 Protocol	Compound No.: Presendin
	Version: 5.0 for EU countries dated 08Dec2022

legal authorities to be included on the grounds that informed consent could not be assumed.

Patients must not be enrolled if they meet any of the following exclusion criteria:

IIH related exclusion criteria:

1. Presence of venous sinus thrombosis on brain imaging by either magnetic resonance or computerised tomographic venography
2. Previous IIH surgery including CSF shunt, optic nerve sheath fenestration or dural venous sinus stent or sub-temporal decompression
3. Previous bariatric surgery within the last 3 months or intention during the trial
4. Abnormal neurological examination (aside from papilloedema and consequent visual loss or sixth or seventh nerve palsy or palsies)
5. Treatment to lower ICP within 1 week prior to screening visit (e.g., acetazolamide, topiramate (including if used as a migraine preventative), diuretics, glucocorticoids (I.V., injectable steroids or oral (including dexamethasone and prednisolone)). (Nasal, inhaled, or topical steroids are allowed)
6. Use of any drugs known to cause intracranial hypertension, including exposure to fluoroquinolones, lithium, vitamin A, or tetracyclines within 2 months prior to diagnostic LP

Vision related exclusion criteria:

7. Any disease other than refractive error that causes visual loss in the study eyes. Where there is uncertainty this would be determined by the Independent Adjudication Committee [IAC]

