- 8 The diagnostic LP will be the baseline LP and must be performed in lateral decubitus position. Patients with ICP <25 cm CSF at diagnosis will be excluded
- 9 Lumbar puncture to be performed after visual assessment. LP to be performed as per Appendix 1. CSF sample from visit 10 LP will be retained for future potential analysis
- 10 Patients will be provided with training on the self-administration of the trial medication. The patient will be asked to self-administer placebo at visit 1 to demonstrate ability to self-inject. Patients who are not comfortable to self-inject will be excluded
- 11 If patients discontinue in the randomised double-blind treatment period they will be encouraged to return for all trial visits up to visit 11. If a patient does not want to return for all visits then they will be asked to return at a minimum for visit 11 procedures for safety follow up
- 12 In the 4 weeks prior to visit 10, patients must not have missed more than one dose of trial medication and must have self-administered their final dose within 7 days of visit 10. Patients will be reminded by the trial site to self-administer trial medication weekly, to continue this until the completion of visit 10 and to bring their trial medication with them at visit 10 for return.  
Where more than one dose has been missed during the preceding 4 weeks, visit 10 should be delayed. Self-administration of trial medication should continue at 7-day intervals and then visit 10 rescheduled to ensure no more than one dose of the trial medication has been missed in the previous 4 weeks. Visit 10 should be delayed no more than 14 days
- 13 Optional unscheduled visit for visual testing (HVF, OCT, LogMAR) for patients in whom there is concern about visual decline or who perform inadequately or where there is technical failure (more than 15% false positive responses or inadequate performance indicated by the Visual Field Reading Centre for HVF; or OCT imaging not of satisfactory quality as determined by the OCT Reading Centre)
- 14 In the event of any abnormal safety assessments identified at end of treatment, e.g., abnormal ECG, abnormal routine laboratory results or ongoing adverse events, this visit may be performed at the clinic to repeat or follow up safety assessments
- 15 Reporting of AEs/SAEs will continue up to the final follow up visit 11

Study Number: INVEX-CLIN-IIH-301 Protocol	Compound No.: Presendin
	Version: 5.0 for EU countries dated 08Dec2022

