The screening period will be followed by a 24-week randomised double-blind treatment period in which patients will be randomised (1:1) to receive a SC dose of either Presendin (containing 2mg of exenatide (active group) or matching placebo (placebo group), self-administered once weekly.

At the end of the randomised treatment period (week 24), all patients will have an end of treatment clinic visit. Five weeks after the end of that treatment visit, an end of trial safety follow-up telephone visit will be performed. In the event of any abnormal safety assessments or ongoing adverse event(s) identified at end of treatment; for example, an abnormal ECG or abnormal routine laboratory results, this visit may be performed at the clinic and a safety follow-up performed as appropriate.

Study Number: INVEX-CLIN-IIH-301 Protocol	Compound No.: Presendin
	Version: 5.0 for EU countries dated 08Dec2022

[figure not shown]
The duration of the randomised treatment period was felt to be appropriate as the previous phase 2 trials of Exenatide in IIH demonstrated efficacy by 3 months. Additionally, an alternative off label drug used in IIH (acetazolamide) was evaluated over a 6-month period. Hence efficacy is relevant over this time frame. A longer period of randomisation would not be ethical if patients were expected to remain on placebo for 12 months as this could place their overall health at risk.

Assessments will be performed as outlined in [Table 1](#).

A schematic diagram of the trial can be seen in [Figure 1](#).

Study Number: INVEX-CLIN-IIH-301 Protocol	Compound No.: Presendin
	Version: 5.0 for EU countries dated 08Dec2022

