### **13.5. Reporting and Handling of Pregnancies**

Pregnant patients will be withdrawn from the trial.

Female patients will be instructed to notify the Investigator immediately if they become pregnant during the trial and up to 12 weeks after discontinuation/completion of trial medication. Pregnant patients will be withdrawn from further trial treatment. The patients will also be instructed to report pregnancies discovered after the last visit, if they believe that conception occurred during their participation in the trial.

A pregnancy as such is not an AE, unless there is a possibility that the trial medication has interfered with the efficiency of any contraceptive measures. The Investigator should report all pregnancies to the Sponsor contact or designee within 24 hours of being informed of them. The pregnancy report form should be used instead of the SAE form.

The pregnant patients will be followed until the end of the pregnancy. Any complication during the pregnancy should preferably be reported as an AE. The outcome of the pregnancy must be reported on the pregnancy report form. Any spontaneous abortion, stillbirth, birth defect/congenital anomaly, death, or other serious infant condition must be reported and followed up as an SAE.

Patients will give consent on enrolment that the Investigator will report any pregnancy to the Sponsor and that further information will be collected until delivery.

Study Number: INVEX-CLIN-IIH-301 Protocol	Compound No.: Presendin
	Version: 5.0 for EU countries dated 08Dec2022

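### Inclusion criteria 9 and 10 place the last follow-up visit 12 weeks after stopping drug, but Visit 11 falls nominally 5 to 6 weeks after a completer's last dose

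*Protocol*

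**What the plan says.** Criterion 9 in Section 5.2.1 requires women of childbearing potential to use highly effective birth control "during the whole trial duration including the last follow-up visit (12 weeks after ceasing drug"). Criterion 10 requires men to "abstain from sperm donation during the trial including the last follow-up visit (12 weeks after ceasing drug") and their partners to use "a highly effective method of contraception during the trial, including the last follow-up visit (12 weeks after ceasing drug"). The protocol summary repeats both criteria.

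The schedule of that visit is given elsewhere:

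- Table 1, footnote 15, identifies the final visit: "Reporting of AEs/SAEs will continue up to the final follow up visit 11".
- Section 4.1.1 sets its timing: "Five weeks after the end of that treatment visit, an end of trial safety follow-up telephone visit will be performed". Table 1 gives Visit 10 as Day 169 (Week 24) and Visit 11 as Day 204 (Week 29).
- Table 1, footnote 12, ties the end of dosing to Visit 10: patients "must have self-administered their final dose within 7 days of visit 10".
- Section 4.1.3 limits participation: "The duration of the trial for each patient will be up to 30 weeks".

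Section 13.5 asks female patients to notify the investigator of a pregnancy during the trial and "up to 12 weeks after discontinuation/completion of trial medication".

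**The concern.** The criterion gives an event (the last follow-up visit) and an interval (12 weeks off drug) as if they were the same point in time. For a completer they are not, so the rule cannot be followed literally: the visit it describes is not in the schedule.

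The rule is an undertaking that patients must give to be eligible. Section 1.1 says the disease is most frequent in women of childbearing age. Section 1.1.2 reports an effect of Byetta on foetal development in animals at three times the human exposure in diabetes treatment. The last scheduled pregnancy test is also at Visit 11 (Table 1, Section 6.1.6), so no later scheduled contact would reveal that contraception had stopped too soon.

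**Working it through.** Only date arithmetic is needed. Inputs from Table 1: Visit 10 on Day 169 (window ±14 days) and Visit 11 on Day 204 (window ±5 days). The last dose is taken as 0 to 7 days before Visit 10 (footnote 12).

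**The plan's other timings reproduce.** 204 − 169 = 35 days = 5 weeks, as in Section 4.1.1. Screening, treatment and follow-up give 1 + 24 + 5 = 30 weeks, as in Section 4.1.3.

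**The 12-week label does not.**

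- Last dose: Day 169 − 7 = 162 to Day 169.
- Last dose to Visit 11: 204 − 169 = 35 days to 204 − 162 = 42 days (5 to 6 weeks). The label says 12 × 7 = 84 days.
- End of 12 weeks off drug: 162 + 84 = Day 246 to 169 + 84 = Day 253.
- Nominal gap after Visit 11: 246 − 204 = 42 days to 253 − 204 = 49 days (6 to 7 weeks).
- Day 246 to 253 is Week 35 to 36 from randomisation, where Visit 11 is Week 29. Counting the screening week, as Section 4.1.3 does, it is Week 36 to 37 against a maximum of 30.

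**Visit windows do not close the gap.** The result depends on whether Visit 11 moves with Visit 10.

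- If Visit 11 is counted five weeks from the actual Visit 10, with ±5 days, the interval from last dose is 35 − 5 = 30 to 42 + 5 = 47 days.
- If Visit 11 stays at Day 204 ± 5 while Visit 10 moves by ±14 days (Day 155 to 183), the last dose lies between Day 148 and Day 183. The interval is then 199 − 183 = 16 to 209 − 148 = 61 days.

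Neither reaches 84 days. If the lumbar puncture is re-booked, Section 6.1.5 keeps the patient on drug, which moves the last dose later and does not lengthen the interval to a fixed Visit 11.

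**Patients who stop drug early but stay in the trial.** With Visit 11 on Day 204, the two dates coincide for a last dose on Day 204 − 84 = 120, about Week 17 (Day 115 to 125 with the Visit 11 window). Before that, 12 weeks ends sooner than the trial does: a patient who stops at Week 4 reaches 12 weeks at Week 16, while Visit 11 is at Week 29. This matters for the replacement wording.

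**Separate minor check.** Section 14.3.4.3 derives BMI after baseline at Weeks 4, 8, 16, 24, 32 and 48. Table 1 measures it at Weeks 4, 8, 12, 16, 20 and 24. Weeks 32 and 48 do not exist in the schedule, and Weeks 12 and 20 are collected but not listed.

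**The case against.** The strongest reply is that this is a mislabelled visit and not a rule with two competing end dates. The 12-week interval is printed every time the rule appears, Section 13.5 uses the same period for pregnancy notification, and nowhere does the protocol state a contraception period of 5 to 6 weeks. To stop early, a site would have to set aside the printed number and look up Visit 11 in Table 1. That reply stands and limits the severity. It does not make the criterion correct: Section 13.5 governs notification, not contraception, and the words about the whole trial and its last visit still point to Visit 11.

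Three stronger readings are tempting and unsupported. A reader might infer that the protocol sets two equally authoritative end dates; the evidence above favours 12 weeks. A reader might infer that patients were released from contraception early; the consent pages are not available, so what patients agreed to, and hence the practical risk, cannot be judged. A reader might infer that the label holds only for a last dose exactly at Week 17; that figure ignores the Visit 11 window and assumes that an early discontinuer attends on Day 204.

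**Conclusion.** The point holds as a low-severity wording error in a safety rule. The gap of 6 to 7 weeks is nominal: it applies to completers and assumes a last dose 0 to 7 days before Visit 10 and visits on their scheduled days. Windows change its size but not the conclusion. A site that follows the printed 12 weeks is unaffected; one that follows the named visit would end the requirement early.

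No estimate, power figure, endpoint or data collection depends on this. The BMI list is a separate minor slip that adds nothing to the severity. It concerns descriptive summaries, and Section 6.3.5 leaves collection to Table 1, so no data are lost.

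**What to change.** In criteria 9 and 10, in the summary and in Section 5.2.1 (six places), remove the reference to the last follow-up visit with its 12-week label. State instead that contraception and abstention from sperm donation apply *throughout the trial and until at least 12 weeks after the last dose of trial medication, whichever is later*. The interval should be confirmed clinically.

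The final clause is needed. Table 1, footnote 11, and Section 12.2.1 encourage patients who stop drug to keep attending. Simply adding an end at 12 weeks after the last dose to the existing whole-trial wording would create a new conflict for those who stop before about Week 17.

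Separately, the BMI list in Section 14.3.4.3 should read Screening, Baseline and Weeks 4, 8, 12, 16, 20 and 24.

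The cost is wording only: no change to visits, sample size or analysis.

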## 5.2.2. Exclusion Criteria

Patients will not be enrolled if they meet any of the following exclusion criteria:

IIH related exclusion criteria:

1. Presence of venous sinus thrombosis on brain imaging by either magnetic resonance or computerised tomographic venography
2. Previous IIH surgery including CSF shunt, optic nerve sheath fenestration or dural venous sinus stent or sub-temporal decompression
3. Previous bariatric surgery within the last 3 months or intention during the trial
4. Abnormal neurological examination (aside from papilloedema and consequent visual loss or sixth or seventh nerve palsy or palsies)
5. Treatment to lower ICP within 1 week prior to screening visit (e.g., acetazolamide, topiramate (including if used as a migraine preventative), diuretics, glucocorticoids (I.V., injectable steroids or oral (including dexamethasone and prednisolone)). (Nasal, inhaled, or topical steroids are allowed)
6. Use of any drugs known to cause intracranial hypertension, including exposure to fluoroquinolones, lithium, vitamin A, or tetracyclines within 2 months prior to diagnostic LP

Vision related exclusion criteria:

7. Any disease other than refractive error that causes visual loss in the study eyes. Where there is uncertainty this would be determined by the Independent Adjudication Committee [IAC]
8. Refractive error worse than +/- 6.00 sphere or worse than +/- 3.00 cylinder in study eyes. In addition, participants with myopia of worse than -6.00 D sphere but less than or equal to -8.00 D sphere are eligible if the subject wears a contact lens for all perimetry examinations with the appropriate correction
9. Inability to perform a reliable visual field examination as deemed by the Visual Field Reading Centre in the study eyes. Where there is uncertainty this would be evaluated by the Independent Adjudication Committee [IAC]

Headache related exclusion criteria:

10. Does not complete  $\geq 6$  days of electronic/paper trial diary during the 7-day screening period

Study Number: INVEX-CLIN-IIH-301 Protocol	Compound No.: Presendin
	Version: 5.0 for EU countries dated 08Dec2022

Other exclusion criteria:

11. Untreated previously diagnosed obstructive sleep apnoea with historically recorded apnoea-hypopnea index greater than 15
12. Glucagon like peptide-1 receptor agonist within last 4 weeks prior to screening
13. COVID-19 vaccine within 2 weeks prior to screening
14. Allergy/known hypersensitivity to the active substance and/or excipients of the investigational product
15. Has known contraindications to glucagon like peptide-1 (GLP-1) receptor agonists (e.g., ketoacidosis, severe gastrointestinal disease, pancreatitis, renal impairment) which may affect the safety of the patient
16. History of drug-induced immune-mediated thrombocytopenia from exenatide products
17. Personal or family history of medullary thyroid carcinoma or in patients with Multiple Endocrine Neoplasia syndrome type 2
18. Using any glucose-lowering medication
19. Currently taking warfarin
20. Alanine transaminase (ALT) or aspartate transaminase (AST)  $\geq 2x$  the upper limit of normal (ULN), total bilirubin  $\geq 1.5x$  ULN, or alkaline phosphatase (ALP)  $\geq 1.5$  ULN at screening (Note – patients with elevated total bilirubin are not excluded if they meet criteria for Gilbert’s syndrome, including: bilirubin is predominantly indirect [with normal direct bilirubin level]; and ALT, AST and ALP  $\leq 1x$  ULN)
21. Kidney disease (as defined by serum cystatin C-based estimated glomerular filtration rate [eGFR]  $< 55$  mL/min/1.73 m^2, calculated at investigator site)
22. Any of the following abnormalities in clinical laboratory tests at screening, as assessed by the central laboratory and confirmed by a single repeat, if deemed necessary: *Hemoglobin*  $< 10$  g/dL ( $< 100$  g/L); *Platelet count*  $< 75 \times 10^9/L$  ( $< 75,000/mm^3$ )
23. Using recreational or illicit drugs at the time of signing the informed consent, or recent history (within the last year) of drug or alcohol abuse or dependence according to the DSM-5 criteria, that in the opinion of the investigator puts the patient at risk
24. Is unable to self-administer the trial medication (or unable to administer trial medication with support) after receiving training during the Screening period

Study Number: INVEX-CLIN-IIH-301 Protocol	Compound No.: Presendin
	Version: 5.0 for EU countries dated 08Dec2022

25. History of any clinically significant disease or disorder that, in the opinion of the investigator, may either put the patient at risk because of participation in the trial or influence the results or the patient's ability to participate in the trial
26. Any contraindication to lumbar puncture procedure in the opinion of the investigator
27. Has participated in any other interventional trial within 1 month prior to the screening visit.
28. Is pregnant or breastfeeding

Note: Use of headache preventative medication is allowed at enrolment (except for Topiramate). Changes to headache preventative medication during the trial should be made in consultation with the IAC – see section [10.1.2](#)

Study Number: INVEX-CLIN-IIH-301 Protocol	Compound No.: Presendin
	Version: 5.0 for EU countries dated 08Dec2022

